Results from clinical trials and other studies demonstrate that the most common toxicities associated with azacitidine are gastrointestinal (nausea, vomiting, diarrhea, constipation, anorexia), constitutional (fatigue, fever, rigors), musculoskeletal and connective tissue (arthralgia, pain in limb, weakness), pulmonary (cough, dyspnea), skin or soft tissue (injection site bruising from SC injection, rash, erythema), and hematologic (neutropenia, anemia, leukopenia). Nausea, vomiting and diarrhea are among the most common adverse effects of azacitidine and appear to be self-limiting with repeated cycles of therapy. Myelosuppression also occurs in a majority of patients, and accounts for the most common reason of dose reduction and treatment termination during clinical trials. Infrequent adverse effects include neuromuscular aches, generalized weakness, renal tubular acidosis, and liver enzyme abnormalities. Erythema and burning at the injection site can occur following SC administration, which usually resolves within 24-72 hours.

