6.4 Definition of DLT

Dose-limiting toxicities (DLTs) will be evaluated during the dose escalation phase of the trial. The period for evaluating DLTs will be from the time of first administration of oral decitabine (ASTX727) until after 28 days after the first dose of oral decitabine (ASTX727), durvalumab (MEDI4736), and tremelimumab combination therapy (end of Cycle 2 (which is the first cycle of the triple combination)).

Subjects who do not remain on the study up to this time for reasons other than DLT will be replaced with another subject at the same dose level. Grading of DLTs will follow the guidelines provided in the Common Terminology Criteria for Adverse Events (CTCAE) version 4.03.

A DLT will be defined as any Grade 3 or higher toxicity that occurs during the DLT evaluation period. Toxicity that is clearly and directly related to the primary disease or to another etiology is excluded from this definition. The following will be DLTs:

- Any Grade 4 irAE
- Any \geq Grade 3 colitis
- Any Grade 3 or 4 noninfectious pneumonitis irrespective of duration
- Any Grade 2 pneumonitis that does not resolve to ≤ Grade 1 within 3 days of the initiation of maximal supportive care
- Any Grade 3 irAE, excluding colitis or pneumonitis, that does not downgrade to Grade 2 within 3 days after onset of the event despite optimal medical management including systemic corticosteroids or does not downgrade to ≤ Grade 1 or baseline within 14 days
- Liver transaminase elevation $> 8 \times ULN$ or total bilirubin $> 5 \times ULN$
- Any ≥ Grade 3 non-irAE, except for the exclusions listed below
- Grade 4 neutropenia lasting > 10 days or accompanied by fever (defined as > 38.5°C requiring

hospitalization)

• Grade 3 thrombocytopenia with clinically significant bleeding

The definition excludes the following conditions:

- Grade 3 fatigue lasting \leq 7 days
- Grade 3 endocrine disorder (thyroid, pituitary, and/or adrenal insufficiency) that is managed
 with or without systemic corticosteroid therapy and/or hormone replacement therapy and the
 subject is asymptomatic
- Grade 3 inflammatory reaction attributed to a local antitumor response (eg, inflammatory reaction at sites of metastatic disease, lymph nodes, etc)
- Concurrent vitiligo or alopecia of any AE grade
- Grade 3 infusion-related reaction (first occurrence and in the absence of steroid prophylaxis) that resolves within 6 hours with appropriate clinical management

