- Grade 3 or 4 neutropenia that is not associated with fever or systemic infection that improves by at least 1 grade within 3 days. Grade 3 or Grade 4 febrile neutropenia will be a DLT regardless of duration or reversibility
- Grade 3 or 4 lymphopenia
- Grade 3 thrombocytopenia that is not associated with clinically significant bleeding that requires medical intervention, and improves by at least 1 grade within 3 days
- Isolated Grade 3 electrolyte abnormalities that are not associated with clinical signs or symptoms and are reversed with appropriate maximal medical intervention within 3 days
- Grade 3 emesis that responds to optimal antiemetic therapy within 72 hours
- Grade 3 diarrhea that responds to optimal medical management within 72 hours

Immune-related AEs are defined as AEs of an immune nature (ie, inflammatory) in the absence of a clear alternative etiology. In the absence of a clinically significant abnormality, repeat laboratory testing will be conducted to confirm significant laboratory findings prior to designation as a DLT.

If a DLT occurs, the patient will be removed from further treatment in the protocol. The patient will be followed for their DLT until there is complete resolution of the observed toxicity. These toxicities will effect dose escalation decisions. Any occurrence of grade 4 or greater toxicity will prompt the sponsor and the principal investigator to conduct a thorough evaluation of the available safety information to justify a decision to enroll new subjects into the study.

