6.5.2 Azacitidine/Oral decitabine (ASTX727)

6.5.2.1 Dose Adjustment Guidelines

Drug Substance Azacitidine/Decitabine (ASTX727)

Study Code 15-11430

Edition Number 13.0

Date 09202024

A maximum of 1 dose reduction will be allowed from the original dose. Please refer to **Table 2** for the dose cohorts.

Azacitidine or oral decitabine may be withheld for up to 7 days between the end of 1 cycle and the start of the next cycle to allow hematologic criteria to recover sufficiently for the next cycle to begin.

The maximum number of days that a azacitidine or decitabine dose may be withheld without requiring a dose reduction is 7 days.

The maximum number of days that azacitidine or oral decitabine may be withheld due to unacceptable toxicity before a subject is permanently discontinued from the study is 14 days.

For the purposes of dose adjustments, unacceptable toxicity will be defined as any AE that is deemed by the Investigator to be related to azacitidine or oral decitabine (ASTX727) that poses a medical risk or substantial discomfort to the subject including, but not limited to, Grade 3 or 4 hematologic or non-hematologic toxicity. Subjects should be discontinued after the 3rd episode.

Please refer to Table 6 for the Dose Adjustment Guidelines due to unacceptable toxicity.

Table 6: Dose Adjustments and Dose Delays for Toxicity

Toxicity	Recommendation	
Grade 2 hematologic toxicity causing delay to the planned start of a Cycle	Hold azacitidine or decitabine until ANC & Platelets \geq 1.0x10 ⁹ /L Delay \leq 7 days, resume azacitidine or decitabine at	
Absolute Neutrophil Count (ANC) $< 1.0 \text{ x}$ $10^9/\text{L}$ Platelets $< 75 \text{ x } 10^9/\text{L}$	same dose Delay $8-14$ days, reduce azacitidine ordecitabine by a dose cohort level Delay ≥ 14 days, permanently discontinue azacitidine or decitabine	
Grade 3 neutropenia or thrombocytopenia causing delay to the planned start of a Cycle ANC 0.5-0.99 x 10 ⁹ /L Platelets 25-49 x 10 ⁹ /L	Hold azacitidine or decitabine until ANC & Platelets recover to ANC $\geq 1.0 \times 10^9 / L$, Platelets $\geq 75 \times 10^9 / L$) Recovery in ≤ 7 days, resume azacitidine or decitabine at same dose Recovery in 8–14 days, reduce azacitidine or	

Date 09202024

Edition Number 13.0

Date 09202024	decitabine by a dose cohort level No recovery by 14 days, permanently discontinue azacitidine or decitabine_	

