Grade 4 neutropenia or thrombocytopenia causing delay to the planned start of a Cycle ANC $< 0.5 \times 10^9/L$ Platelets $< 25 \times 10^9/L$ For ANC $< 0.5 \times 10^9/L$ The initiation of G-CSF is left at the Investigator's discretion. If initiated administer G-CSF per institutional practice or package insert and continue until ANC recovers to $\ge 2.0 \times 10^9/L$	Hold azacitidine or decitabine until ANC & Platelets recover to \leq Grade 1 (ANC \geq 1.5 x 10^9 /L, Platelets \geq 75 x 10^9 /L) Recovery in \leq 7 days, reduce azacitidine or decitabine by a dose cohort level No recovery by 7 days, permanently discontinue azacitidine or decitabine	
Grade 3 or 4 Nausea or Vomiting Grade 3 or 4 Diarrhea Grade 3 or 4 Fatigue/Asthenia	Hold until resolution to ≤ Grade 1 and provide optimal medical management. If response ≤ 72 hours (3 days), and recovery ≤ 7 days, reduce azacitidine or decitabine by a dose cohort level If event recurs after re-challenge at reduced dose, discontinue azacitidine or decitabine. If no recovery by 7 days, discontinue azacitidine or decitabine.	
Grade 3 or 4 any other non-hematologic toxicity	Hold until resolution to ≤ Grade 1 and provide optimal medical management. If recovery ≤ 7 days, reduce azacitidine or decitabine by a dose cohort level. If event recurs after re-challenge at reduced dose, discontinue azacitidine or decitabine If no recovery by 7 days,	

Date 09202024

Date 0/202021				
	discontinue azacitidine or			
	decitabine			

ANC = absolute neutrophil count; ASCO = American Society of Clinical Oncology; ESMO = European Society for Medical Oncology; G-CSF = granulocyte colony stimulating factor.

Note: The initiation of G-CSF is left at the Investigator's discretion.

Note: Granulocyte colony stimulating factor (G-CSF) should only be utilized in accordance to ASCO or ESMO recommendations.

Note: If Grade 3 or 4 neutropenia associated with fever or Grade \geq 3 thrombocytopenia with clinically significant bleeding occurs at any time, the dose adjustment guidelines for Grade 4 hematological toxicity should be enacted.

Note: If neutropenia is associated with fever and severe diarrhea, subject should be managed appropriately according to the local practice. In case of recurrence of the diarrhea with neutropenia and fever, the continuation of the subject in the study should be discussed on a case-by-case basis with the sponsor's study monitor.

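### Section 6.4 excludes some Grade 3 platelet and GI events as DLTs on a 3-day test alone, so a later permanent ASTX727 stop for the same event goes unscored in the 2-of-6 rule

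*Combined protocol and SAP*

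**What the plan says.** Section 6.4 starts from a broad default: "Any ≥ Grade 3 non-irAE, except for the exclusions listed below" is a DLT. The exclusions that follow set a short test. Low platelets are left out by this wording: "Grade 3 thrombocytopenia that is not associated with clinically significant bleeding that requires medical intervention, and improves by at least 1 grade within 3 days". Neutrophils have a separate item that extends one severity level higher: "Grade 3 or 4 neutropenia that is not associated with fever or systemic infection that improves by at least 1 grade within 3 days". Among GI events, diarrhea has its own item, which reads "Grade 3 diarrhea that responds to optimal medical management within 72 hours", with parallel wording for emesis of that grade.

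Table 6 in 6.5.2.1 governs ASTX727 dosing after toxicity and uses different clocks. Its Grade 3 hematologic row applies when the event delays a cycle start. It holds drug until ANC is at least 1.0 and platelets at least 75 (x 10^9/L), and ends with "No recovery by 14 days, permanently discontinue". The Grade 4 row needs ANC of at least 1.5 and platelets of at least 75, and ends with "No recovery by 7 days, permanently discontinue azacitidine or decitabine". A further row covers GI symptoms and fatigue of Grades 3 and 4; it requires a return to Grade 1 or lower, and otherwise says "If no recovery by 7 days, discontinue azacitidine or decitabine". The text of 6.5.2.1 also caps holding for unacceptable toxicity at 14 days, after which the subject leaves the study.

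The escalation rule (3.1, 6.2, 6.3 and 11) counts DLTs only; two or more in a cohort of six stops it. Section 6.4 replaces a subject who leaves before the end of the DLT window for a reason other than a DLT. The closing text of 4.2 says withdrawn patients are not replaced.

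**The concern.** The two sets of rules measure the same event differently. The 6.4 exclusions ask whether it began to improve in 3 days. Table 6 asks whether it recovered by day 7 or 14. An event can pass the first test and fail the second. The patient then loses the study drug to drug toxicity during the DLT window, and nothing in the protocol makes that stop a DLT.

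The 2-of-6 rule is the only numeric safety criterion for moving from Days 1-3 to Days 1-4 to Days 1-5. Myelosuppression is an expected toxicity of this drug class. Section 1.4.2.5 says of azacitidine, the trial's other hypomethylating agent: "Myelosuppression also occurs in a majority of patients, and accounts for the most common reason of dose reduction and treatment termination during clinical trials". A patient who cannot start Cycle 2 because platelets stay low would therefore be informative for the escalation decision but would add nothing to the count. Adverse-event reporting for the secondary objective is unaffected.

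**Working it through.** **Step 1: which events fall between the two rules.** Cut-offs are those printed in Table 6 (Grade 3 platelets 25-49, Grade 3 ANC 0.5-0.99, Grade 4 ANC below 0.5).

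| Event | Section 6.4 | Table 6 | Gap? |
|---|---|---|---|
| Platelets 40 at planned Cycle 2 start, 55 by day 3, no bleeding, still below 75 at day 14 | Excluded (one grade better) | Permanent stop at 14 days | Yes |
| Grade 3 emesis, or Cycle 1 diarrhea, responding by 72 hours but still Grade 2 at day 7 | Excluded (*responds* is not defined) | Discontinue at 7 days | Yes |
| Afebrile ANC 0.4, then 0.7 by day 3, then 1.2 on day 7 | Excluded on one reading | Permanent stop at 7 days (needs 1.5) | Arguable |
| Grade 3 neutropenia alone | Excluded if one grade better, i.e. ANC at least 1.0 | Resumes at ANC 1.0 | No |
| Grade 4 thrombocytopenia, febrile neutropenia, or Grade 3/4 neutropenia or thrombocytopenia not improving in 3 days | DLT | Any action | No |

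Table 6's GI row itself treats response within 72 hours and recovery within 7 days as separate conditions, so the protocol does not equate the two.

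**Step 2: how the patient is then counted.** If ASTX727 stops before the first combination dose, the end of the DLT window (28 days after that dose) is never reached. Under 6.4 the patient is replaced and leaves both numerator and denominator. Under 4.2 the patient is not replaced; if kept in the cohort, the patient counts as a non-DLT. The stop is unscored either way.

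**Step 3: illustrative size.** The protocol states no operating characteristic for the 2-of-6 rule (the probabilities in Section 11 concern the BED), so there is no figure to reproduce. Let d be the rate of DLTs as now listed and u the rate of unscored stops, taken as mutually exclusive. Both are assumptions. With X ~ Bin(6, p), a cohort passes with probability P(X <= 1) = (1-p)^6 + 6p(1-p)^5, where

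- replaced: p = d/(1-u);
- kept as non-DLT: p = d;
- counted as DLT: p = d + u.

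| d | u | Replaced | Kept | Counted | Replaced minus counted |
|---|---|---|---|---|---|
| 10% | 1% | 0.884 | 0.886 | 0.866 | 0.018 |
| 10% | 3% | 0.880 | 0.886 | 0.822 | 0.057 |
| 20% | 1% | 0.650 | 0.655 | 0.631 | 0.020 |
| 20% | 3% | 0.640 | 0.655 | 0.582 | 0.058 |

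Differences are taken before rounding. Worked line: d = 0.10, u = 0.03 gives p = 0.10/0.97 = 0.103 if replaced and p = 0.13 if counted. Counted, 0.87^6 + 6 x 0.13 x 0.87^5 = 0.434 + 0.389 = 0.822.

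Measured against keeping the patient, the difference is 0.020 to 0.073. Replacement slightly lowers the pass probability compared with keeping, so the effect comes from not scoring the event rather than from replacing the patient. A cohort of six contains at least one such stop with probability 1-(1-u)^6, which is 0.059 at u = 1% and 0.167 at u = 3%.

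**The case against.** **Section 6.5.2.2 points the other way.** It covers azacitidine or decitabine, never stops treatment at 14 days, and defines recovery as nadir + 0.5 x (baseline - nadir). For the platelet example with the lowest eligible baseline of 100, that is 40 + 0.5 x 60 = 70. A count of 55 is not recovered, but the action is a dose reduction. For the neutropenia example with baseline ANC 1.5 to 2.0, recovery is 0.95 to 1.2, so 1.2 on day 7 already counts as recovered. This stands. The gap opens only where Table 6 or the 14-day limit in 6.5.2.1 governs, and the protocol does not say which prevails. A dose reduction alone is not claimed to be a DLT.

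**The neutropenia case is contestable.** After improving to Grade 3 on day 3, the residual Grade 3 neutropenia could itself be read as a DLT if it persists. Section 6.4 also requires a full safety evaluation after any Grade 4 event. This stands, so the point rests on platelets and GI events.

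**Diarrhea in Cycle 2.** Once durvalumab starts, 6.5.1 treats enterocolitis symptoms without another cause as immune-related. The Grade 3 irAE rule in 6.4 then applies, and it has a 14-day test. This stands, and is why the diarrhea gap is mainly in Cycle 1.

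**DLT rules and dosing guidance need not coincide.** Table 6 is headed as recommendations, and toxicity review before escalation (6.3) and the DSMC (Section 13) can act on judgement. That is fair, but these reviews have no numeric criterion, and the Grade 4 trigger misses Grade 3 platelet and GI events. For Grade 3 irAEs, 6.4 already pairs a 3-day test with a 14-day one, so a second test follows the sponsor's own approach.

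**Stronger inferences the documents do not support.** A reader might infer that persistent cytopenias generally escape the DLT count. They do not, because the default in 6.4 captures most of them. A reader might also infer that the plan overstates its chance of passing a cohort by 10 to 20 points. That needs unscored stop rates of 5% to 10%, for which there is no support, and the plan states neither a pass probability nor a target DLT rate that could be overstated.

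**Conclusion.** The point holds, within limits. Grade 3 thrombocytopenia that improves one grade within 3 days, and Grade 3 emesis or (mainly Cycle 1) diarrhea that responds within 72 hours, can end in a permanent ASTX727 stop that the 2-of-6 rule never sees. Afebrile Grade 4 neutropenia is a weaker case and is not needed for the conclusion.

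The frequency is unknown. The course is compound (early improvement, then a stall), so low rates are the sensible illustration. At an assumed 1% to 3%, not scoring the stop raises the pass probability by about 2 to 6 points if patients are replaced and 2 to 7 if they are kept. The conclusion also assumes that Table 6 or 6.5.2.1 prevails over 6.5.2.2. Severity is minor to moderate: the effect is on the escalation decision only, and the correction needs no new data.

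**What to change.** 1. Add to the 6.4 cytopenia and GI exclusions a condition that the event does not lead to permanent discontinuation of ASTX727 under 6.5.2.1/Table 6 within the DLT window. State that a Grade 3 or higher ASTX727-related event that does so counts as a DLT, and that a stop before the first combination dose is within the window. Limiting this to events that reached Grade 3 keeps investigator-judged discomfort, which 6.5.2.1 admits as unacceptable toxicity, out of the count.
2. Limit replacement for the DLT assessment to departures unrelated to study-drug toxicity, and make 4.2 agree with 6.4. Extra subjects may still be added for evaluable biopsy pairs.
3. Choose one action at 14 days: Table 6 stops the drug, 6.5.2.1 takes the subject off study, and 6.5.2.2 reduces the dose. Correct the Table 6 Grade 2 row as well: it resumes at platelets of at least 1.0 x 10^9/L and lists ANC below 1.0, which the next row grades 3.

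**Cost.** Cohorts would stop somewhat more often. Compared with replacement, P(stop) rises from 0.116 to 0.134 (d = 10%, u = 1%), from 0.120 to 0.178 (10%, 3%) and from 0.360 to 0.418 (20%, 3%). A stop at level 1 means six more patients on Days 1-2; a stop at level 2 ends escalation. Under 6.4 and item 6 of 4.3 a DLT ends all protocol treatment, so a reclassified patient would also lose durvalumab. The protocol describes no durvalumab-alone path for the decitabine cohorts; whether to allow one is the sponsor's decision and not a required part of this change.

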4.3 Withdrawal of Subjects from Study Treatment and/or Study

Permanent discontinuation of study treatment

An individual subject will not receive any further investigational product if any of the following occur in the subject in question:

- 1. Withdrawal of consent or lost to follow-up
- 2. Adverse event that, in the opinion of the investigator or the sponsor, contraindicates further dosing

Drug Substance Azacitidine/Decitabine (ASTX727)

Study Code 15-11430

Edition Number 13.0

Date 09202024

- 3. Subject is determined to have met one or more of the exclusion criteria for study participation at study entry and continuing investigational therapy might constitute a safety risk
- 4. Pregnancy or intent to become pregnant
- 5. Any AE that meets criteria for discontinuation as defined in Section 10.3.
- 6. Dose-limiting toxicity (See Section 5.5 for definition of DLT)
- 7. Grade \geq 3 infusion reaction
- 8. Subject noncompliance that, in the opinion of the investigator or sponsor, warrants withdrawal; eg, refusal to adhere to scheduled visits
- 9. Initiation of alternative anticancer therapy including another investigational agent
- 10. Confirmation of PD and investigator determination that the subject is no longer benefiting from treatment with azacitidine, durvalumab (MEDI4736), and tremelimumab

Subjects who are permanently discontinued from further receipt of investigational product, regardless of the reason (withdrawal of consent, due to an AE, other), will be identified as having permanently discontinued treatment.

Subjects who are permanently discontinued from receiving investigational product will be followed for safety per Section 10.0 and Appendix 1 or 2, including the collection of any protocol-specified blood specimens, unless consent is withdrawn or the subject is lost to follow-up or enrolled in another clinical study. All patients including those who discontinue protocol therapy early, will be followed for response until first disease progression and survival until 24 months from study registration. All subjects will be followed for survival. Subjects who decline to return to the site for evaluations will be offered follow-up by phone every 3 months as an alternative.

Withdrawal of consent

If consent is withdrawn, the subject will not receive any further investigational product or further study observation.

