6.1.2 Procedures for randomization

This is not a randomized study. All eligible subjects will be allocated, by non-random assignment, to trial treatment and will receive a unique number. This unique number is termed a randomization number throughout the protocol for operational purposes. The randomization number identifies the subject for all procedures occurring after treatment allocation. Once a randomization number is assigned to a subject, it can never be re-assigned to another subject.

A single subject cannot be assigned more than one unique number. Treatment assignment will be done based on the schema described in **Sections 3.2 and 6.2, Table 2**. All patients will receive the same fixed dose of durvalumab (MEDI4736) and tremelimumab (based on a weight greater than 30 kg) and oral decitabine (ASTX727) will be dose escalated if safe to do so. Enrolled patients will be sequentially assigned to the cohorts. After the enrollment of 6 evaluable patients into the 1st group (eligible patients who at least begin protocol treatment and have an evaluable pre- and on-treatment (8-week) biopsy sample available), the next 6 patients will be enrolled into the 2nd cohort if safe to do so. After the enrollment of 6 evaluable patients into the 2nd cohort, the next 6 patients will be enrolled into the 3rd cohort only if the BED has not been determined, and the group in which the BED has been determined will be expanded to enroll 10 patients. Additional subjects may be enrolled into the cohort(s) to ensure that the required number of evaluable pre- and on-treatment biopsy samples are available to adequately determine the BED. Patients cannot change groups or dose assignments upon the initiation of the study protocol.

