in bowel habits, medical intervention indicated, peritoneal signs; Grade 4 Colitis: lifethreatening consequences, urgent intervention indicated)

(Grade 3 Perforation: severe symptoms, elective* operative

intervention indicated; Grade 4 Perforation: life-threatening consequences, urgent intervention indicated)

Grade 3

Permanently discontinue study drug/study regimen for Grade 3 if toxicity does not improve to Grade ≤1 within 14 days; study drug/study regimen can be resumed after completion of steroid taper.

Grade 4

Permanently discontinue study drug/study regimen.

For Grade 3 or 4:

- Promptly initiate empiric IV methylprednisolone 2 to 4 mg/kg/day or equivalent.
- Monitor stool frequency and volume and maintain hydration.
 - Urgent GI consult and imaging and/or colonoscopy as appropriate.
 - If still no improvement within 3 to 5 days of IV methylprednisolone 2 to 4 mg/kg/day or equivalent, promptly start further immunosuppressives (e.g., infliximab at 5 mg/kg once every 2 weeks). Caution: Ensure GI consult to rule out bowel perforation and refer to infliximab label for general guidance before using infliximab. If perforation is suspected, consult a surgeon experienced in abdominal surgery immediately without any delay.
- Once the patient is improving, gradually taper steroids over
 ≥28 days and consider prophylactic antibiotics, antifungals, and
 anti-PJP treatment (refer to current NCCN guidelines for
 treatment of cancer-related infections).^a

*This guidance anticipates that Grade 3 operative interventions of perforations are usually not elective

Hepatitis (elevated LFTs)

Date 09202024

Infliximab should not be used for management of immune-related hepatitis.

PLEASE SEE
shaded area
immediately below
this section to find
guidance for
management of
"Hepatitis (elevated
LFTS)" in HCC
patients

Any Elevations in AST, ALT or TB as Described Below

AST or ALT >ULN
and ≤3.0×ULN if
baseline normal, 1.53.0×baseline if
baseline abnormal;
and/or TB > ULN and
≤1.5×ULN if baseline
normal, >1.01.5×baseline if

baseline abnormal

as v

No dose modifications. If it worsens, then treat as described for elevations in the row below.

General Guidance

AST or ALT >3.0×ULN and ≤5.0×ULN if baseline normal, >3-5×baseline if baseline abnormal; and/or TB >1.5×ULN and ≤3.0×ULN if baseline

- Hold study drug/study regimen dose until resolution to AST or ALT ≤3.0×ULN and/or TB ≤1.5×ULN if baseline normal, or to AST or ALT ≤3.0×baseline and/or TB

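### For some events that Section 6.4 defines as DLTs, Sections 4.3 and 6.4 end treatment while Table 6 or Appendix 1 continues it, and no passage says which rule prevails

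*Combined protocol and SAP*

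**What the plan says.** **Stop.** Section 4.3 lists the events after which a subject receives no further investigational product. Item 6 is "Dose-limiting toxicity (See Section 5.5 for definition of DLT". The contents list no Section 5.5; the definition is in 6.4. Section 6.4 repeats the rule without exception: "If a DLT occurs, the patient will be removed from further treatment in the protocol".

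**Continue.** Three groups of events that 6.4 makes DLTs are treated differently elsewhere.

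- *Febrile neutropenia and bleeding thrombocytopenia.* Section 6.4: "Grade 3 or Grade 4 febrile neutropenia will be a DLT regardless of duration or reversibility". It also lists Grade 3 thrombocytopenia with clinically significant bleeding. A note to Table 6 (6.5.2.1) says that if either "occurs at any time, the dose adjustment guidelines for Grade 4 hematological toxicity should be enacted". The Grade 4 row then says, for recovery within 7 days, to "reduce azacitidine or decitabine by a dose cohort level".
- *Non-immune toxicity.* Section 6.4 includes "Any ≥ Grade 3 non-irAE, except for the exclusions listed below". For other Grade 3 or 4 non-hematologic toxicity, Table 6 holds the drug and reduces it by a cohort level if recovery takes 7 days or less. The non-immune table in Appendix 1 resumes Grade 3 events that settle within its limits.
- *Grade 3 colitis.* Section 6.4 makes any colitis of Grade 3 or higher a DLT. The colitis guidance in Appendix 1 requires permanent discontinuation only if there is no improvement to Grade 1 or less within 14 days; otherwise "study drug/study regimen can be resumed after completion of steroid taper".

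**Scope.** Section 6.5.2.3 allows resumption after a toxicity interruption at any point in the first 12 months, which includes the DLT window (Cycles 1 and 2).

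**Dose assignment.** Section 6.1.2 says "Patients cannot change groups or dose assignments upon the initiation of the study protocol", and 3.1 and 6.2 say nearly the same. Section 6.5.2.1 allows one dose reduction.

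**The concern.** Two sets of instructions cover the same patient in the same weeks. One ends all protocol treatment; the other holds, reduces or resumes it. A site that opens 6.4 and a site that opens Table 6 would both believe they were following the protocol. In a study whose secondary objective is safety, that is enough to need correcting.

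The primary objective is also touched. Sections 6.1.2 and 11 define a patient as evaluable for the BED if protocol treatment was begun and an evaluable pre-treatment and on-treatment 8-week biopsy pair exists. Section 8.3.3.2 describes the biopsy of a patient who stops early as post-treatment. So the section followed can decide whether a DLT patient's Week 8 sample is on-treatment. Nothing says to which dose level a sample belongs if the schedule was reduced before it was taken.

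**Working it through.** **1. The rules side by side, for an event in Cycle 1 or 2**

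| Event (a DLT in 6.4) | 4.3 item 6 and 6.4 | Other passage |
|---|---|---|
| Grade 3-4 febrile neutropenia | remove | Table 6 note, Grade 4 row: reduce if recovered in 7 days or less |
| Grade 3 thrombocytopenia with significant bleeding | remove | same |
| Non-excluded Grade 3 or higher non-hematologic, non-immune toxicity related to decitabine | remove | Table 6: hold, then reduce if recovered in 7 days or less; Appendix 1: Grade 3 may resume |
| Grade 3 colitis | remove | Appendix 1: resume after taper if Grade 1 or less within 14 days |

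**2. How many patients.** Section 6.3 closes a cohort at two DLTs, so a cohort not closed has at most one DLT patient: 1/6 = 17%. The documents give no DLT rate. If the true rate is d, the chance of exactly one DLT in six, given fewer than two, is 6d/(1 + 5d). For assumed d of 10%, 20% and 30% this is 0.6/1.5 = 40%, 1.2/2.0 = 60% and 1.8/2.5 = 72%. These are upper limits for this point, because only some DLTs fall in the table above.

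**3. Exposure before the Week 8 biopsy.** Decitabine is taken on the first days of each cycle and Cycle 3 starts at Week 8. I assume the biopsy precedes Cycle 3 dosing. For level B2 (Days 1-4):

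- No change: 4 + 4 = 8 tablets.
- DLT in Cycle 1 after its tablets, reduced to B1 for Cycle 2: 4 + 3 = 7.
- Same DLT, removed: 4.
- DLT after the Cycle 2 tablets: 8 under either rule.

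Full B1 exposure is 3 + 3 = 6. Exposure therefore differs only if the DLT precedes completion of Cycle 2 decitabine. Durvalumab is given at Week 4 and next at Week 8, and Appendix 1 tapers steroids over at least 28 days. Colitis starting after the Week 4 infusion therefore cannot lead to a different durvalumab exposure before Week 8.

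**4. The plan's own operating figures (Section 11).** At a true BED rate of 50%:

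- P(at least 2 of 6) = 1 - 7/64 = 0.891; the plan states .89.
- P(at least 2 of 6, then at least 7 of 16) = sum over x = 2 to 6 of b(6, x) × P(Y ≥ 7 - x), with Y binomial(10, 0.5), = 0.735; the plan states .73. The match is to this joint probability, although the column heading is worded as conditional.

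**5. Sensitivity to one patient, same 50% rate**

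| Handling of the one DLT patient | at least 2 responders | two-stage | at least 3 responders (written 50% rule) |
|---|---|---|---|
| Removed and made up to six evaluable | 0.891 | 0.735 | 0.656 |
| Removed and not made up, or counted as a non-responder | 1 - 6/32 = 0.812 | 0.632 | 0.500 |
| Kept on the reduced schedule, assumed response probability 0 to 0.5 | 0.812 to 0.891 | 0.632 to 0.735 | 0.500 to 0.656 |

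One patient's handling moves the first-stage figure by up to 8 points and the two-stage figure by up to 10.

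**The case against.** The best defence is that the texts have different force. Sections 4.3 and 6.4 are mandatory and specific to DLTs; Table 6 is a guideline with a recommendation column, and Appendix 1 is generic, with pediatric and liver-cancer sections. DLTs are assessed only in dose escalation through Cycle 2, so Table 6 would keep plenty of scope for non-DLT toxicity, later cycles, the expansion cohort and azacitidine patients. That is sensible, but it is not written anywhere. The Table 6 note applies whenever the event occurs, and 6.5.2.3 covers the whole first year.

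Other parts of the defence stand and limit the point:

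- A reader might infer that every non-excluded Grade 3-4 non-hematologic toxicity is in conflict. It is not. Table 6 covers only events the investigator relates to azacitidine or decitabine, and it stops that drug without recovery by 7 days. Appendix 1 also stops treatment for Grade 3-4 pneumonitis, for transaminases above 8×ULN and for most Grade 4 immune events.
- A reader might infer that a removed patient is always lost to the BED. Section 6.3.1 speaks of an 8-week post-baseline sample without requiring it to be on-treatment, early stoppers are biopsied, and 6.1.2 and 11 allow extra subjects to complete the evaluable pairs. But that enrollment is optional, and it does not classify a reduced patient's sample.
- The sentence on not changing groups or dose assignments can be read as barring moves between cohorts. It is in tension with 6.5.2.1 but does not plainly forbid every reduction.

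**Conclusion.** The contradiction is in the current text and should be corrected. For the events listed, the protocol gives opposite instructions and no order of precedence.

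Its statistical reach is narrow. In a cohort not closed by the two-DLT rule it concerns at most one patient in six: the on-treatment status of one Week 8 sample and, only for a DLT before Cycle 2 decitabine is completed, the exposure behind it. The DLT count and the two-DLT stopping rule do not depend on how the patient is managed afterwards.

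It would be tempting to conclude that the BED decision for a dose level turns on the section followed. The documents do not show that: they give neither a DLT rate nor a response rate on a reduced schedule. The ranges above rest on assumed values and show only that a change is possible.

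**What to change.** 1. Reconcile 4.3 item 6, 6.4, 6.5.2 with Table 6, 6.5.2.3 and Appendix 1. Add one statement of which rule governs an event that meets the DLT definition, and make the other passages match. The clinical team decides which rule stands. Correct the cross-reference in item 6.
2. Reword the sentence on changing groups or dose assignments in 3.1, 6.1.2 and 6.2 so that it agrees with whatever reductions are kept.
3. In 6.1.2 and 11, before the BED review, state how the Week 8 biopsy of a DLT patient or a reduced-schedule patient is counted, and with which denominator; 6.3.1 refers to patients treated, 6.1.2 and 11 to evaluable patients. Counting by assigned level keeps every patient but mixes exposures. Setting such patients aside and replacing them gives cleaner exposure but conditions the result on tolerating the schedule. It would also have to be squared with the end of 4.2 (withdrawn patients not replaced) and with 6.4 (only non-DLT dropouts replaced). Either is defensible if fixed beforehand.

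The cost is amendment wording. No new assessments are needed, and the planned sample size need not change.
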